6.2. Second-period Endpoints

- 1. Changes in 6MWD from enrollment to week 24
- 2. Changes in QOL from enrollment to week 24

- 3. Change in NYHA class from enrollment to week 24
- 4. Changes in dyspnea using Borg scale from enrollment to week 24
- 5. Changes in dyspnea using UCSD SOBQ from enrollment to week 24
- Changes in O₂ desaturation measures (time, distance, recovery time) during 6MWT from enrollment to week 24
- 7. Changes in FVC, DLco from enrollment to week 24
- Changes from enrollment in resting PaO₂, SpO₂, SaO₂, and A-a gradient from enrollment to week 24
- 9. Changes in BNP level from enrollment to week 24
- 10. AEx of IPF
- 11. Number of all-cause hospitalizations
- 12. Survival time

6.3. Acute Exacerbations

The following 3 criteria will define AEx in subjects with acute worsening of their respiratory conditions:

- 1. Clinical (all of the following required):
 - A) Unexplained worsening of dyspnea or cough within 30 days, triggering unscheduled medical care (eg clinic, study visit, hospitalization)
 - B) No clinical suspicion or overt evidence of cardiac event, pulmonary embolism, or deep venous thrombosis to explain acute worsening of dyspnea
 - C) No pneumothorax
- 2. Radiologic/Physiologic (only 1 of the following required):
 - A) New ground-glass opacity or consolidation on computed tomography (CT) scan or new alveolar opacities on chest x-ray
 - B) Decline of \geq 5% in resting room air SpO2 from last recorded level OR decline of \geq 8 mm Hg in resting room air PaO2 from last recorded level
- 3. Microbiologic (all of the following required):
 - A) No clinical evidence for infection (ie, absence of grossly purulent sputum, fever > 39°C orally)

B) No microbiologic evidence of infection (ie, clinically significant bacterial growth on sputum or endotracheal aspirate cultures, quantitative culture by protected brush specimen $\geq 10^3$ cfu/mL or bronchoalveolar lavage $\geq 10^4$ cfu/mL or the presence of specific pathogens on stains of any of the above)

6.4. Identification of Acute Exacerbation

All subjects will be educated regarding the importance of identifying AEx. At the time of enrollment, subjects will be educated to the possibility of developing acute symptomatic worsening that might represent an AEx of IPF and instructed to contact their study site coordinator within 48 to 72 hours of the apparent event.

All subjects will be questioned about any change in dyspnea or cough and any interim clinic visits or hospitalizations. Finally, as part of the IPFnet outreach to community referring-physicians, the importance of AExs will be emphasized. When a subject is identified who meets criteria 1A, this will trigger the collection of additional clinical data to evaluate a suspected AEx. These data will be collected as part of standard clinical care (i.e., this protocol does not require collection of all items). Items collected as part of standard of care for suspected AEx include:

- IPFnet AEx case report form (CRF) (required)
- Chest x-ray, CT scan with/without pulmonary angiogram (reports should be faxed and followed by hard copies or discs)
- Oxygen saturation (pulse oximetry)
- ABG
- Respiratory cultures (sputum, endotracheal aspirate, and lavage)
- Blood cultures
- Clinic/hospital records related to the event

All potential cases of AEx will be reviewed by the site PI first, and a decision on whether the case may represent an AEx will be made. If AEx is suspected, the case will be sent to the IPFnet Adjudication Committee, which will assign a final diagnosis (see Table 5). If there is disagreement among members, the majority opinion will be recorded.

[figure not shown]
During episodes of suspected AEx, as determined by the individual site investigator, treatment with study drug will be withheld. Subjects will remain blinded and in the study unless the attending physician responsible for the subject's acute medical care and the DCC medical monitor feel unblinding is needed for subject safety reasons.

Definite acute exacerbation	All criteria met; no alternative etiology	
Unclassifiable acute	Insufficient data to evaluate all criteria; no alternative	
worsening	etiology	
Not acute exacerbation	Alternative etiology identified that explains acute worsening	

 Table 5: Final Diagnoses in Evaluation of Suspected Acute Exacerbations

An AEx will be treated at the discretion of the treating physician. Standard of care generally involves evaluation for respiratory infection, pulmonary embolism, cardiac events, and pneumothorax; and treatment with intravenous corticosteroids. Because the standard of care for management of suspected AExs includes steroids, the following dose will be recommended: intravenous solumedrol—1.0 g/day (4 equally divided doses) for 3 days, 0.5 g/day (2 equally divided doses) for 3 days, and 1.0 mg/kg/day for 3 days, with subsequent 0.5 mg/kg/day of oral prednisone tapered off over the remainder of 2 weeks.

Study drug will be resumed at presuspected AEx doses after subjects clinically improve, as confirmed by the local PI. Subjects unable to return to the study site after suspected AEx due to medical frailty (eg, continued institutionalization and progressive disability) will be categorized as failing to improve 20% on 6MWD in secondary analyses.

Acute Exacerbation Management Algorithm

Figure 6.1: Acute Exacerbation Flow Chart

7. SAFETY ASSESSMENTS

7.1. Adverse Events

During a clinical trial, the reporting of adverse event information can lead to important changes in the way a new treatment is developed, as well as provide integral safety data.

7.2. Definitions

An adverse event (AE) is any untoward medical occurrence in clinical-investigation subject administered a pharmaceutical product. An AE does not necessarily have a causal relationship with this study drug. An AE can, therefore, be any unfavorable and unintended sign (including an abnormal laboratory finding, for example), symptom, or disease temporarily associated with the use of a medicinal product, whether or not considered to be related to the medicinal product. Diseases, signs, symptoms, or laboratory abnormalities already existing at enrollment are not considered AEs unless they worsen (ie, increase in intensity or frequency). Surgical procedures themselves are not AEs; they are therapeutic measures for conditions that require surgery. The condition for which the surgery is required

may be an AE. Surgical procedures planned prior to randomization and the conditions leading to these measures are not AEs.

A serious adverse event is any untoward event that:

- is fatal
- is life-threatening
- requires inpatient hospitalization or prolongation of existing hospitalization, with the following exceptions:
 - Preplanned (prior to the study) hospital admissions unless the hospitalization is prolonged
 - Planned admissions (as part of a study, eg, routine biopsies)
 - o 23-hour rehospitalizations
 - Hospitalization for elective procedure
 - Emergency room visits
- results in persistent or significant disability or incapacity
- is a congenital anomaly or birth defect
- important medical events that may not result in death, be life-threatening, or require inpatient hospitalization may be considered an SAE when, based on appropriate medical judgment, they may jeopardize the subject and may require medical or surgical intervention to prevent one of the outcomes listed above.

Life-threatening means that the subject was, in the view of the investigator, at immediate risk of death from the AE as it occurred. It does not include an AE that, had it occurred in a more severe form, might have caused death.

Persistent or significant disability/incapacity means that the event resulted in permanent or significant and substantial disruption of the subject's ability to carry out normal life functions.

Associated with the use of the drug means that there is a reasonable possibility that the experience may have been caused by the drug.

7.3. Adverse Event Collection

For the IPFnet STEP-IPF trial, all AEs (serious and nonserious) will be recorded from start of study treatment through final study visit on the AE CRF. All SAEs will be recorded from start of study treatment through 28 days after discontinuation of study drug.

7.4. Procedures for Reporting a Serious Adverse Event

For the IPFnet STEP-IPF trial, all deaths and all SAEs require expedited reporting. The investigator must complete and submit a Pfizer Investigator Initiated Research (IIR) form to DCRI Safety Surveillance within 24 hours of knowledge of the event.

DCRI Safety Surveillance [contact] [contact]

The investigator must complete and submit a follow-up IIR form when important follow-up information (diagnosis, outcome, results of specific investigations, etc.) becomes available after submission of the initial form. Follow-up forms should be submitted according to the same process used for reporting the initial event as described above (ie, within 24 hours of knowledge). All reportable events will be followed until resolution, stabilization, or 30 days after the last subject enrolled has completed their last study visit, whichever occurs first. The investigators will be responsible for reporting AEs to their local institutional review boards (IRBs) in accordance with local guidelines.

DCRI Safety Surveillance will forward the IIR forms to the DSMB chair, the NHLBI representative and Pfizer U.S. Clinical Safety within 1 to 2 business days.

Regulatory Reporting

AEs that meet the criteria of serious, study drug-related, and unexpected per the U.S. package insert, qualify for expedited reporting to the regulatory authorities. The DCRI Safety Surveillance Medical Monitor will perform a medical review of all SAEs submitted and evaluate for "unexpectedness." DCRI Safety Surveillance will confirm unexpectedness of the

event with the site. Site investigators are required to complete and submit the voluntary form 3500 MedWatch online for the events identified as serious, drug-related, and unexpected at https://www.accessdata.fda.gov/scripts/medwatch/.

7.5. Unblinding Procedures

The DCC Medical Monitor will be available to the study physician to help consider the need for unblinding on a case-by-case basis. Unblinding will be permitted ONLY for subject safety. Specifically, the blind should be broken only for serious, unexpected, and drug-related AEs or when required by local regulatory authorities, when the knowledge of treatment assignment is needed for subject safety. The site investigator must notify the DCC before unblinding any subject. The site investigator must notify the Medical Monitor at the DCC to begin the unblinding process for any subject. In an emergency, if the clinical center investigator is not immediately available, the attending physician may contact the DCC Medical Monitor directly. Emergency contact wallet cards will be provided to all study subjects.

Contact Information for DCC Medical Monitor(s): [contact]

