5.6.1 Contraindications

Hypersensitivity to sildenafil or any component of the formulation; concurrent use of organic nitrates (nitroglycerin) in any form (potentiates the hypotensive effects)

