5.6.3 Study Drug Discontinuation

Study drug will be stopped in any subject with SBP < 100 mm Hg or DBP < 50 mm Hg. Subjects with chest pain, palpitations, worsening peripheral edema, S3 gallop, or diaphoresis will have a 12-lead ECG and a 2D-echocardiogram performed as soon as possible. Study

drug will be stopped in subjects with acute coronary syndromes, AV block, life-threatening arrhythmias, left ventricular dysfunction (EF < 25%), or clinically significant visual changes.

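### Section 7.5 adds the regulatory-reporting criteria to the safety test for unblinding, so, read literally, an emergency judged unrelated to drug would not qualify

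*Protocol*

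**What the plan says.** Section 7.5 begins by making the DCC Medical Monitor available to discuss each case, and sets the general rule: "Unblinding will be permitted ONLY for subject safety". The next sentence narrows it: "Specifically, the blind should be broken only for serious, unexpected, and drug-related AEs", with a regulatory demand as the alternative and a closing clause about safety need. In full, the permitted circumstances are "for serious, unexpected, and drug-related AEs or when required by local regulatory authorities, when the knowledge of treatment assignment is needed for subject safety". The section then provides an emergency route. If the site investigator cannot be reached at once, "the attending physician may contact the DCC Medical Monitor directly", and every subject carries an emergency contact card.

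Four other places bear on this:

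- Section 7.4 sends to regulators those AEs that are "serious, study drug-related, and unexpected per the U.S. package insert".
- Section 6.4 keeps subjects with a suspected acute exacerbation blinded unless the attending physician and the DCC medical monitor "feel unblinding is needed for subject safety reasons".
- Section 5.6.1 lists as a contraindication "concurrent use of organic nitrates (nitroglycerin) in any form (potentiates the hypotensive effects".
- Section 5.6.3 foresees coronary events on study: "drug will be stopped in subjects with acute coronary syndromes". It does not mention unblinding.

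**The concern.** A reporting test and an unblinding test answer different questions. The first decides which events a regulator must hear about quickly, so it looks for harms that are new and attributable to the drug. The second should ask whether the treating physician must know the assignment to manage the subject. An event can need that knowledge while being wholly unrelated to study drug, or while being a recognised reaction to it.

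The practical case is a blinded subject with acute coronary symptoms, for whom the physician is considering a nitrate. A Medical Monitor who applies the *Specifically ... only* sentence as written could conclude that the event does not qualify, while the sentence before it says that safety decides. The physician can presume sildenafil exposure and withhold nitrates. That protects subjects on active drug, but a subject on placebo might then go without a treatment that is not contraindicated.

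**Working it through.** No figure is in dispute, so the check is a comparison of texts.

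**1. Structure of the 7.5 sentence.** It names two routes: (a) an AE that is serious and unexpected and drug-related, or (b) a regulatory requirement. The clause on safety need follows a comma with no *or*. It may qualify both routes or only the second, but on either parse it is not a third route. The preceding sentence requires safety need in any case. Route (a) therefore asks for the three adjectives and safety need together. Route (b) does not help at the bedside.

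**2. Source of the adjectives.** Section 7.4 uses the same three terms for expedited reporting and ties *unexpected* to the U.S. package insert. Section 7.5 gives no definition of its own.

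**3. An acute coronary event under route (a).**

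| Causality judgement | Drug-related? | Unexpected? | Qualifies, read literally? |
|---|---|---|---|
| Unrelated | No | Not reached | No |
| Related | Yes | Depends on the package insert, not shown | No if listed there; yes if not, given seriousness and safety need |

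The first row needs no outside source. For the second, Section 5.6 lists angina pectoris, myocardial ischemia and MI among reported reactions, which suggests that such an event would count as expected. Section 5.6 does not say, however, that its list is the package insert's list, so this row stays unverified.

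**4. Does the assignment matter to treatment?** Section 5.6.1 contraindicates nitrates with sildenafil, and Section 5.6.3 anticipates acute coronary syndromes. Stopping study drug, as 5.6.3 requires, does not tell the physician whether the subject has already been exposed.

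**5. Comparison with 6.4.** For suspected exacerbations the criterion is a safety judgement shared by the attending physician and the medical monitor, with no test of expectedness or causality. Section 6.4 is the specific rule for those subjects and would normally govern.

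**6. Who could be affected.** The issue arises only in the blinded period, 12 of the 24 treatment weeks, because all subjects then receive open-label sildenafil. Section 5.3 excludes angina that limits the walk test (criterion 4), MI in the past 6 months (7), nitrate use (8) and life-threatening arrhythmia within 1 month (11). Section 5.6.2 adds that unstable cardiovascular disease is excluded. No criterion excludes stable coronary disease as such. The documents give no coronary event rate for this population, so no expected count can be derived.

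**The case against.** The strongest answer is that 7.5 should be read as a whole. It speaks of case-by-case consideration, makes safety the governing idea, says *should* in the restrictive sentence, opens a direct line for an attending physician in an emergency, and issues contact cards to every subject. An emergency route has little use if expectedness and causality must be settled first. On that reading the closing clause expresses the real test, and the rest is clumsy drafting.

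Most of this stands. It rules out several stronger conclusions that a reader might infer:

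- *That emergency unblinding is missing.* The route is there and was plainly intended.
- *That the reporting test replaces safety.* Safety need remains a condition; the reporting criteria are added to it.
- *That no coronary event could ever qualify.* This would require knowing that the package insert lists the event, and the insert is not shown.
- *That subjects with a suspected exacerbation are barred from unblinding.* Section 6.4 gives them their own route.

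What the answer does not remove is the word *only* in a sentence introduced by *Specifically*. The emergency line and the cards give access to the Medical Monitor; they do not change the criterion that the Monitor is told to apply. An event judged unrelated still falls outside that criterion on its literal terms.

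**Conclusion.** The point holds as a minor drafting fault and is a cheap improvement. Two adjacent sentences of 7.5 state different tests, and the narrower one borrows criteria made for regulatory reporting. Read literally, it excludes an event judged unrelated to drug even where the assignment would guide treatment. Its exclusion of a related event is conditional on the package insert.

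The size is small. Few subjects are likely to be affected, though that is a judgement from the entry criteria and the 12-week window and not an estimated rate. Harm would also require a Monitor to follow the narrow sentence over the general one. The primary endpoint and its analysis are not affected. The conclusion rests on a literal reading of the restrictive sentence; a Monitor guided by the section as a whole would probably unblind.

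**What to change.** In Section 7.5, replace the three-part condition so that the blind may be broken *when knowledge of the treatment assignment is needed for the subject's safety or acute medical management, as judged by the treating physician with the DCC Medical Monitor, or when required by regulatory authorities*. Keep the three-part test in Section 7.4 only, where it serves reporting. A cross-reference from 6.4 to 7.5 would be a useful tidy-up, so that both sections visibly apply one rule.

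The cost is one sentence, and optionally the cross-reference, in a protocol amendment. The downside is possibly a few more code breaks during the 12 blinded weeks, each still passing through the Medical Monitor.

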8. STUDY DRUG PROCEDURES

At the baseline, 6-week, 12-week, and 18-week study visits, subjects will receive a supply of study drug sufficient to last for 6 weeks.

9. DATA MANAGEMENT

9.1 Hardware and Software Configuration

9.1.1. Hardware and Database Software

Data will be stored in an Oracle database system. Oracle has advantages of processing efficiency and smooth linkage with other software systems. The application and database will be hosted on Solaris Unix servers at the DCC. Clintrial will be used for data entry.

9.1.2. Statistical Software

SAS will be used as the principal application for the management of analysis data files and statistical computations. S-Plus will be used to provide supplementary functions as needed.

9.1.3. Access Control and Confidentiality Procedures

Access to databases will be controlled centrally by the DCC through user passwords linked to appropriate privileges. This protects the data from unauthorized changes and inadvertent loss or damage.

9.1.4. Security

Database and Web servers will be secured by a firewall and through controlled physical access. Oracle has many security features to ensure that any staff member accessing the database has the proper authority to perform the functions he or she requests of the system. Within the secondary SAS databases, Unix group-access control maintains similar security. The Sun workstation login is secured by extensive user-password facilities under Unix.

9.1.5. Back-up Procedures

Database back-up will be performed automatically every day, and standard DCC policies and procedures will be applied to dictate tape rotation and retention practices.

9.1.6. Virus Protection

All disk drives that provide network services, and all user computers, will be protected using virus-scanning software. Standard DCC policies will be applied to update these protection systems periodically throughout the study.

9.2. Sources of Data

Data will be captured and forwarded to the DCC from the sites and the adjudication committees. First, basic clinical information, (eg, demographic information), will be recorded on paper CRFs and forwarded via parcel-delivery service to the DCC for data entry.

9.3. Data Management Activities

In general, the following data management procedures will be applied:

- Paper CRFs will be designed specifically for the needs of this study. The CRF will be partitioned into "booklets" according to the type of data captured (eg, screening and clinical data). Identification information will identify key fields, eg, the participant's ID number, initials, and date of birth, as well as the date of the evaluation.
- The CRF will be printed on 3-part NCR paper. At regular intervals, the different parts of the CRF will be separated. One part will remain at the clinical sites while the others will be forwarded to the DCC using a parcel-delivery system.
- 3. Personnel at clinical sites will record the data mandated by the protocol on the CRFs. They will be abstracted from the participant's medical charts and other source documents. All CRFs will be completed according to the current Good Clinical Practice (GCP) guidelines. Training on completing the CRFs will be included in the training session described in the IPFnet STEP-IPF MOOP.
- 4. A database will be created on the DCRI computer network specifically for this study. As described above, the database will be managed with Oracle using Clintrial.
- 5. For every record type, the data dictionary will identify key fields (eg, the participant's ID number and the type and date of evaluation), the field type (eg, numeric, character, checklist, or date), and ranges for impossible and improbable values.
- 6. All CRFs will be entered into the study database. Double data-entry by 2 different operators will be performed to ensure a high level of confidence in the data entered.

A series of computerized validation checks will be performed at the DCC. "Queries" will be generated, and data clarification forms (DCFs) for problems and exceptions uncovered will be forwarded to the clinical sites for investigation and resolution. Corrections will be made on the DCF using current GCP standards and forwarded to the DCC. If corrections are needed to the CRF form prior to the initial submission to the DCC, a single line will be drawn through the original entry such that the original entry is still visible. The correct value will be written close to the field and the correction initialed and dated by the IPFnet staff member making the change.

